5.7.1.2. Modified Weekly Schedule (Days 1, 8 and 15, Every 28 Days)

For logistical reasons such as holidays, Day 1 delays in the scheduled study treatment for up to 3 days is permitted. Additionally, shifts in the start of a new cycle by -1 or up to +3 days will be permitted in Cycles \geq 3. If patients do not meet retreatment criteria on Days 8 and 15 of a given cycle, the dose should be omitted. A delay of 1 day in the dosing of Days 8 and 15 is permitted; if a delay occurs, subsequent dosings on that cycle should be shifted by 1 day. Intervals <7 days between dosings are not permitted. The start of the next cycle should remain the same.

ImmunoGen, Inc. Confidential Page 64 of 138

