1. INTRODUCTION

1.1. Background

IMGN853 0401 is an open label, non-randomized, first-in-human (FIH), dose-escalation and dose-expansion Phase 1 study. It is designed to identify the maximum tolerated dose (MTD) of IMGN853 when administered intravenously as a single agent in adult patients with relapsed or refractory epithelial ovarian cancer (EOC) and other FOLR1-positive solid tumors (dose escalation) and enable further evaluation of the recommended Phase 2 dose (RP2D). The safety, tolerability, pharmacokinetics (PK), pharmacodynamics (Pd), immunogenicity, and preliminary anti-tumor activity of IMGN853 will be characterized.

During dose escalation two dosing schedules were evaluated: Schedule A (IMGN853 administered on Day 1, with cycles repeating every 21 days (Q3W)) and Schedule B (IMGN853 administered on Days 1, 8, and 15, with cycles repeating every 28 days). Dose expansion began once the Schedule A MTD was identified and a dose was selected for further exploration. Schedule B evaluation was stopped prior to identifying the MTD

The purpose of this Statistical Analysis Plan (SAP) is to outline the statistical principles which will be used to analyze and present the data from this study. This SAP includes a description of the study endpoints, stopping rules, and analysis populations. Table, Figure, and Listing shells will be supplied in a separate document. The SAP may be modified until the time of data base lock. Any deviations from the SAP, including any deviations after the time of database lock, will be documented in the study report.

The protocol for IMGN853 0401 describes the general approach to analysis of data from the study. This Statistical Analysis Plan is based on [Amendment 10](#) of Clinical Study Protocol IMGN853 0401. A brief history of the protocol amendments is presented in Table 1.

Table 1: History of Protocol and Amendments to the Protocol

Version	Approval Date	Changes Expected to Impact the SAP
Protocol	01Mar2012	
Amendment 1	13Apr2012	Lowered starting dose, added additional escalation cohort
Amendment 2	18Oct2012	Endometrioid endometrial cancer was added to the list of tumors that could be enrolled without proof of FOLR1+.
Amendment 3	07Mar2013	Secondary endpoints PFS, TTP, and DoR added.
Amendment 4	13May2013	Assay for Circulating Tumor Cells (CTCs) and other Pd assessments added

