3.7.1. Safety Population

The Safety Population will consist of all patients who received at least one dose of study drug.

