3.8. Data Display Characteristics

Data displays produced for this study will include data listings, summary tables, and figures. Unless stated otherwise, data listings will be produced for all recorded data. Summary tables will be produced as specified in following sections. Additional data listings will be produced for outcome measures that involve extensive procedures to derive the analyzed outcomes. Figures will be produced when specified in sections to follow. Final delivery of tables, listings, and figures will have numbering in compliance with the ICH E3 guideline. Prior to compilation of the clinical study report, Novella standard TREF, FREF, and LREF reference numbers will be used.

Data listings will simply list the data recorded in the eCRF or derived for each patient. They will be ordered by phase (escalation or expansion), cohort, patient number, and time of assessment. When expedient, additional levels of ordering hierarchy may reflect subsets of assessments within patient. Data listings will not display patient initials.

Summary tables will display summary statistics calculated for each of the dose cohorts or treatment groups, unless described otherwise in following sections. See shell tables for specific formats.

The summary statistics displayed will be a function of the type of data associated with the summarized assessment. For categorical variables, the number and percent of each category within a parameter will be calculated. For continuous variables, the sample size (n), mean, median, and standard deviation, as well as the minimum and maximum values, will be presented. Some continuous variables may also be grouped into categorical levels and evaluated in frequency tables.

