6. SAFETY ANALYSES

Safety analyses will use data from the Safety population. Patients will be analyzed according to the actual study treatment received.

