6.1. Exposure

Exposure to IMGN853 will be summarized with descriptive statistics for the number of doses received, the number of cycles received, duration of dosing (weeks, calculated as [date of last dose – date of first dose + 21]/7 for Schedule A, and [date of last dose – date of first dose + 14]/7 for Schedule B), total cumulative dose (mg), dose intensity (mg/kg AIBW Q3W, calculated as [total cumulative dose (mg) / {baseline AIBW (kg) * duration of dosing (weeks)/3}]), and relative dose intensity (%), calculated as [dose intensity/ 6] *100).

The number of infusions with dose decreased, infusions interrupted, and dose delayed will also be summarized by cohort. The number of infusions with the rate of infusion decreased will also be summarized by cohort.

Listings will be provided with the information from all of the study drug administration eCRFs. A further listing reporting the exposure measures above will be provided.

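### Relative dose intensity in SAP 6.1 is divided by 6 for every treated patient, so as a rule it equals delivered over planned dose only for patients assigned 6 mg/kg AIBW every three weeks whose dosing weight is not revised

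*SAP*

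**What the plan says.** SAP 6.1 builds the measure in three steps: a duration of dosing in weeks, a dose intensity, and the relative figure.

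- Duration adds 21 days after the last dose on Schedule A. On Schedule B it is "date of last dose – date of first dose + 14]/7 for Schedule B".
- Dose intensity is cumulative mg divided by baseline AIBW and by duration/3, in mg/kg AIBW per three weeks, for both schedules.
- The last step is "relative dose intensity (%), calculated as [dose intensity/ 6] *100".

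On scope, SAP 6 states "Safety analyses will use data from the Safety population", and SAP 3.7.1 states "The Safety Population will consist of all patients who received at least one dose of study drug". Nothing in 6.1 limits the ratio to one dose, schedule or phase, and no other planned dose is defined. SAP 6.1 also asks for a listing of the exposure measures.

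For presentation, SAP 3.8 states "Summary tables will display summary statistics calculated for each of the dose cohorts or treatment groups", and SAP 6.1 adds "The number of infusions with dose decreased, infusions interrupted, and dose delayed will also be summarized by cohort". SAP 1.1 notes that "Table, Figure, and Listing shells will be supplied in a separate document"; those shells were not available here.

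**The concern.** Dose intensity is already on a common scale across dose levels and schedules. The further step to a relative figure is therefore naturally read as the share of the planned dose that was delivered. With a divisor of 6 for everyone, it is that share only for patients whose plan was 6 mg/kg AIBW every three weeks. Escalation patients had other plans: the initially planned Schedule A levels in SAP Table 2 run from 0.15 to 9.0 mg/kg and do not include 6, and Schedule B gave three doses per 28 days.

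At stake is the reading of the exposure tables and listing. A fully dosed escalation patient can appear under-dosed, and a reduction can be hidden, so compliance cannot be read from this measure across dose levels or schedules.

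**Working it through.** **Inputs.** Formulas: SAP 6.1. Schedule B regimen and planned levels: SAP 2.3.1.2 and Table 3. Schedule B 2.0 mg/kg: Protocol 4.1.3.2. Weight basis before Amendment 5: SAP 2.3.1.1, Table 2 footnote. AIBW formula and the rule on revising weight for a change of at least 10%: Protocol 5.8.4. Weight range 48.2 to 135.8 kg in the 5 mg/kg group: Protocol 1.10.1. Planned numbers: Protocol 4.1.1. Below, d is the assigned mg/kg per dose and n the number of cycles; DI is dose intensity and RDI relative dose intensity. All doses are given in full on the nominal calendar unless stated.

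**1. Schedule A, AIBW dosing.** Weeks = (21(n − 1) + 21)/7 = 3n. DI = dn/(3n/3) = d. RDI = 100d/6.
- The plan's own reference case reproduces: d = 6 gives DI 6.0 and RDI 100%.
- d = 5.0 gives 83%.

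**2. Schedule B, whole cycles.** Weeks = (28(n − 1) + 14 + 14)/7 = 4n. DI = 3dn/(4n/3) = 2.25d. RDI = 37.5% per mg/kg.

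| d (mg/kg) | RDI by SAP 6.1 |
|---|---|
| 1.1 | 41% |
| 1.8 | 68% |
| 2.0 | 75% |
| 2.5 | 94% |

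A reading of 100% would need 6/2.25 = 2.67 mg/kg, which is not a listed level.

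**3. Schedule B, by last dose given (d = 2.0).**
- Cycle 1 Day 1: 14 days; 2/(14/21)/6 = 50%.
- Cycle 1 Day 8: 21 days; 4/(21/21)/6 = 67%.
- Cycle 1 Day 15: 28 days; 6/(28/21)/6 = 75%.
- Cycle 2 Day 1: 42 days; 8/(42/21)/6 = 67%.

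The calendar windows move it further. Protocol 5.7.1.2 says "shifts in the start of a new cycle by -1 or up to +3 days will be permitted in Cycles" from 3 onward. If every such cycle starts 1 day early, three cycles last 28 + 27 + 14 + 14 = 83 days and read 18/(83/21)/6 = 75.9%, with a limit of 21/27 = 77.8%. If every such cycle starts 3 days late, they last 87 days and read 72.4%, with a limit of 21/31 = 67.7%.

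**4. Actual-weight dosing at 5 mg/kg.** Height and sex are not given, so assume a woman of 160 cm: IBW = 0.9 × 160 − 92 = 52, and AIBW = 52 + 0.4(W − 52).
- W = 48.2: AIBW 50.48; 5 × 48.2/50.48/6 = 80%.
- W = 70 (assumed): AIBW 59.2; 98.5%, close to 100% by coincidence.
- W = 135.8: AIBW 85.52; 132%.

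Over assumed heights of 150 to 175 cm the two extremes become 69–89% and 121–141%.

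**5. A hidden reduction (illustration, dosing weight equal to AIBW).** Two cycles at 7 and two at 5 mg/kg: the SAP gives (24/4)/6 = 100%; delivered over planned is 24/28 = 85.7%.

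**6. Expansion at 6 mg/kg AIBW.** Exact unless dosing weight is revised, because the divisor keeps baseline AIBW. For an assumed 160 cm woman going from 70 to 63 kg, AIBW falls from 59.2 to 56.4, so full later doses read 56.4/59.2 = 95%.

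**7. Patients.** Escalation 44 + 25 = 69; expansion 40 + 20 + 20 + 20 + 40 = 140; total 209. At most 69/209 = 33% have a divisor that is not their planned dose, less any escalation patients treated at 6 mg/kg AIBW.

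**The case against.** The strongest reply is that 6 is a deliberate reference. SAP 6.1 never defines the measure as delivered over planned, and dividing by 6 gives a coherent index of exposure relative to the Schedule A MTD, which the protocol equates with the RP2D. On that view a label in the table shells would settle the matter. Part of this stands: the shells may carry such a label, and the share-of-plan reading is an inference from the word *relative*. But the SAP text does not state the index reading, and that index adds nothing to a dose intensity already in mg/kg AIBW per three weeks. A label would also leave the actual-weight mismatch and the flat 14 days in place. The latter is strictly a fault in the duration definition and would survive any divisor.

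The second reply is that harm is limited. This largely stands. Summaries are by dose cohort or treatment group, and dose decreases, interruptions and delays are counted separately. Within one AIBW-dosed Schedule A level the error is the constant d/6, so it can be undone by division. It cannot be undone that way for actual-weight patients or for Schedule B, and cohort counts do not correct the per-patient listing.

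A reader might infer that exposure reporting as a whole is unsound, or that dose selection is touched. The documents support neither: the planned expansion dose is 6 mg/kg AIBW every three weeks, and the measure feeds no decision rule. A reader might also try to refine the patient count from reported group sizes. Those give 3 or 9 patients at 3.3 mg/kg (Protocol 1.10.1 and SAP 2.3.1.2) and no size for the 5 mg/kg AIBW cohort foreseen in Protocol 1.10.1, so nothing firmer than up to 69 can be stated.

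**Conclusion.** The point holds as a minor, descriptive defect. As written, the rule gives misleading share-of-plan values for escalation patients not assigned 6 mg/kg AIBW every three weeks, with agreement elsewhere only by coincidence. Because of the weight mismatch and the Schedule B duration rule, the size of the error varies between patients.

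The 140 planned expansion patients are affected only where dosing weight is updated under the 10% rule. The compliance figures in steps 1 and 2 assume AIBW dosing, baseline weight throughout, the nominal calendar and, on Schedule B, whole cycles. The actual-weight figures also rest on assumed height and sex, and their end points are the extremes of one 10-patient group.

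**What to change.** Define RDI (%) = 100 × mg delivered / mg planned. Planned mg is the mg/kg assigned at enrollment × the weight in force for dosing at each planned dose, summed over planned doses. That weight is actual weight before Amendment 5 and AIBW after it, updated whenever the protocol's 10% rule is applied.

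- **Schedule A:** planned doses = duration of dosing in weeks/3, keeping the 21 added days. Count the first patient's 28-day Cycle 1 (Protocol 4.1.3.1) as one cycle.
- **Schedule B:** planned doses = 3 × (actual cycle length in days/28) for each cycle before the last, plus the scheduled doses in the last cycle up to and including the last dose given. Cycle length runs from one Day 1 to the next.

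Checks on Schedule B:
- Compliant patients stopping at Cycle 1 Day 1, 8 or 15, or at Cycle 2 Day 1, all give 100%.
- A 14-day delay to Cycle 2, two full cycles: 6/(3 × 42/28 + 3) = 6/7.5 = 80%, where SAP 6.1 gives 60% at 2.0 mg/kg.
- One omitted Day 8 dose in two cycles: 5/6 = 83%.
- 2.0 mg/kg reduced to 1.8 in Cycle 2: 11.4/12 = 95%.

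Check on Schedule A: the first patient, dosed on Days 1, 29 and 50, has (10 − 1)/3 = 3 planned doses and 3 given, so 100%.

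Use of the permitted cycle-start shifts will still move the Schedule B figure slightly off 100%. As now, doses omitted after the last one given are not counted. If exposure relative to 6 mg/kg every three weeks is also wanted, report it separately under that explicit label.

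The cost is a short SAP edit and reprogramming, with no new data.

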6.2. Adverse Events

Adverse event (AE) data are available to ImmunoGen from two sources, the eCRFs and the serious adverse event (SAE) forms. While SAE reconciliation will be performed, the production of data summaries and listings will be based on the data collected on the eCRF.

Treatment-emergent adverse events (TEAEs) are defined as adverse events with an onset date on or after the first dose of study drug, and within 28 days of the last dose of study drug. The adverse events will be coded using MedDRA (version 18.1 or later), associating lower-level terms with preferred terms and system organ classes by the primary hierarchy. The tables will display the counts and percentages of patients who reported at least one TEAE in each system organ class represented in the AE data. Within each system organ class, the tables will display the counts and percentages of patients reporting at least one TEAE as designated by the preferred terms.

The following TEAEs are of special interest:

- Ocular TEAEs
 - This subset includes TEAEs meeting criteria for the following terms: keratopathy and blurred vision. A list of preferred terms for keratopathy will be provided and finalized by the Sponsor before the final database lock.
- Peripheral Neuropathy
 - A list of preferred terms for peripheral neuropathy will be provided and finalized by the Sponsor before the final database lock.
- Pneumonitis

The following AE tables will be produced:

- An Overall Summary of Safety will summarize the numbers of patients with TEAEs by cohort and CTCAE grade and the number of patients who died during the study or within 28 days of last dose.
- All TEAEs
- TEAEs related to IMGN853. This table will include TEAEs with a drug relationship of “Possibly Related” or “Definitely Related.” It will also include TEAEs with missing drug relationships. An AE reported by a patient more than once will be included in this table if at least one of the drug association grades is one of the grades listed here.
- Serious TEAEs
- Serious, Related TEAEs. This subset includes all serious TEAEs with a drug relationship of “Possibly Related” or “Definitely Related.” It will also include serious TEAEs with missing drug relationships. An AE reported by a patient more than once will be included in this table if at least one of the drug association grades is one of the grades listed here.
- Grade 3 or above TEAEs
- Treatment related \geq Grade 3 TEAEs
- TEAEs leading to drug withdrawal. This subset includes TEAEs with an Action Taken of “Drug Permanently Discontinued.”
- Related TEAEs leading to drug withdrawal.
- TEAEs leading to dose delay.
- TEAEs leading to dose reduction.
- TEAEs leading to dose delay or dose reduction.
- Related TEAEs leading to dose delay.
- Related TEAEs leading to dose reduction.
- Related TEAEs leading to dose delay or dose reduction.
- All deaths as well as deaths on Study or within 28 Days of the Last Dose
- Treatment related TEAEs leading to death on study or within 28 days of Last Dose
- Ocular TEAEs
 - Incidence and CTCAE grade of ocular TEAEs
 - Time to first onset of ocular TEAEs
 - Action taken (none, interruption, dose reduction or delay, discontinuation) due to ocular TEAEs
- Peripheral Neuropathy

Subgroup analyses of TEAEs for the patients in EOC expansion cohorts (cohorts 1, 3, and 5) will be performed on the following patient subgroups:

- Patients in EOC expansion cohorts 1, 3, and 5 by platinum resistant status (platinum resistant vs platinum sensitive).
- Patients who are platinum resistant in EOC expansion cohorts 1, 3, and 5 by number of prior regimens (1-3 vs >3).
- Patients who are platinum resistant in EOC expansion cohorts 1, 3, and 5 by FR α percent staining at intensity 2+ (PS2) (25-49%, 50-74%, 75-100%, 50 – 100%).

In addition, TEAEs and related TEAEs will be summarized for patients in EOC expansion cohorts (1, 3, and 5) who are platinum resistant and who have received 1-3 prior lines of therapy and whose FR α percent staining at intensity 2+ (PS2) is 50-100%.

The following AE listings will be produced:

- All pre-treatment AEs will be listed.
- All AEs, sorted by cohort and chronologically within patient. This listing includes system organ class, preferred term, onset and end dates, and other relevant information.
- Serious TEAEs, sorted by cohort and chronologically within patient.
- TEAEs leading to drug withdrawal. This subset includes TEAEs with an Action Taken of “Drug Permanently Discontinued.”
- TEAEs related to study drug. This listing will include TEAEs with a drug relationship of “Possibly Related” or “Definitely Related.” It will also include TEAEs with missing drug relationships.
- Serious TEAEs related to study drug. This listing will include serious TEAEs with a drug relationship of “Possibly Related” or “Definitely Related.” It will also include serious TEAEs with missing drug relationships.
- TEAEs resulting in death. This listing includes TEAEs with a Common Terminology Criteria for Adverse Events (CTCAE) v4.03 Grade of “Grade 5 (Death)”.
- Ocular TEAEs
- Neuropathy TEAEs
- Pneumonitis TEAEs

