2.3. Secondary Objectives

- Evaluate the safety and tolerability of IMGN853
- Evaluate the effectiveness of primary, prophylactic steroid eye drops in preventing or lessening keratopathy and/or blurred vision
- Characterize the PK of IMGN853 when administered intravenously
- Describe any preliminary evidence of IMGN853 antitumor activity
- Characterize the immunogenicity of IMGN853

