 - c. Patients must have measurable or non-measurable disease (such as large masses that cannot be accurately measured) per RECIST Version 1.1. (Appendix E).

- F. **Dose Expansion Cohort 5:** Patients enrolled in this cohort will receive corticosteroid eye drops as primary prophylaxis to assess whether this treatment reduces the risk or severity of blurred vision and/or keratopathy observed in patients treated with IMGN853.
 - a. Patients must have one of the following pathologically documented, definitively diagnosed tumor types:
 - i. Advanced EOC
 - ii. Primary peritoneal cancer
 - iii. Fallopian tube cancer
 - b. Patients must have received at least 3 but not more than 4 prior systemic treatment regimens.
 - c. Patients must meet the minimum requirement of FOLR1 positivity by IHC (≥25% of tumor staining at ≥2+ intensity).
 - d. Patients with primary platinum refractory disease (those who have not responded to a platinum-based regimen or experienced disease recurrence within three months of completing their first platinum-based regimen) are excluded.
 - e. Patients with clear cell or low grade ovarian cancer are excluded.
 - f. Patients must be willing and able to self-administer low-dose corticosteroid eye drops four times daily, for the first 10 days of each cycle, during active study treatment.
 - g. Patients must have measurable or non-measurable disease (such as large abdominal masses that cannot be accurately measured) per RECIST 1.1 (Appendix E).

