4.1.5. Dose Expansion Cohorts

Once the MTD is established, additional patients will be treated in a dose expansion phase that is designed to further evaluate safety and tolerability, assess preliminary efficacy at the MTD, and characterize IMGN853 Pd.

Data obtained in the dose expansion phase will help define the RP2D.

Expansion Cohort #1 will enroll 40 patients with platinum-resistant EOC, primary peritoneal cancer or fallopian tube cancer who have tumors that meet the requirement of FOLR1 positivity by IHC (\geq 25% of tumor staining at \geq 2+ intensity). The size of this cohort was increased to

ImmunoGen, Inc. Confidential Page 61 of 138

better define the frequency and assess the impact of the proposed management guidelines for ocular adverse events.

Expansion Cohort #2 will enroll 20 patients with advanced, recurrent uterine cancer; eligible patients will have tumors with an H score \geq 100 for FOLR1 expression by IHC.

Expansion Cohort #3 will enroll 20 patients with relapsed EOC; eligible patients will have tumors that meet the requirement of FOLR1 positivity by IHC ($\geq 25\%$ of tumor staining at $\geq 2+$ intensity).

Expansion Cohort #4 will enroll 20 patients with relapsed/refractory NSCLC adenocarcinoma or BAC; eligible patients will have tumors that meet the requirement of FOLR1 positivity by IHC (\geq 25% of tumor staining at \geq 1+ intensity).

Expansion Cohort #5 will enroll 40 patients with relapsed EOC, primary peritoneal cancer or fallopian tube cancer who have tumors that meet the requirement of FOLR1 positivity by IHC (\geq 25% of tumor staining at \geq 2+ intensity). Patients enrolled into this cohort will self-administer corticosteroid eye drops four times daily, for the first 10 days of each cycle, to assess whether prophylaxis with topical steroids prevents or lessens severity of ocular toxicity.

In addition to FOLR1-positivity, all patients enrolled in the expansion cohorts must meet all other eligibility criteria (Section 3.1.1). Safety will be evaluated continuously, separately, and in aggregate in the expansion cohorts. If at any time $\geq 33\%$ of patients treated in an expansion cohort experiences a Cycle 1 DLT, further enrollment to that cohort will stop and a CRC will be convened. The CRC will review all available safety data and PK data to determine how further dosing should proceed. If it is decided that a new dose should be investigated, enrollment to the cohort will begin anew.

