5.8.2. Premedication with Corticosteroid Eye Drops (Dose Expansion Cohort#5 ONLY)

All patients enrolled into Cohort Expansion 5 will be instructed to self-administer 1% prednisolone (Pred Forte[®] or generic equivalent) six times daily on Days 1-5 and four times daily on Days 6-10 of each cycle during the study (Figure 4).

[figure not shown]
These medications will be prescribed by the treating physician and will be sourced by the site. Patients will record their eye drop administration in a patient diary, which will be entered on the CRF.

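### The SAP's EOC safety subgroups pool Cohort 5, the only cohort given prophylactic steroid eye drops, with Cohorts 1 and 3, so the ocular comparison by platinum status is mixed with drop use by design

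*SAP*

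**What the plan says.** SAP 6.2 sets up the EOC safety subgroups on the three ovarian cohorts together: "Subgroup analyses of TEAEs for the patients in EOC expansion cohorts (cohorts 1, 3, and 5) will be performed on the following patient subgroups". The first subgroup is "Patients in EOC expansion cohorts 1, 3, and 5 by platinum resistant status (platinum resistant vs platinum sensitive"), and the second is "Patients who are platinum resistant in EOC expansion cohorts 1, 3, and 5 by number of prior regimens (1-3 vs >3"). Bands of FRα percent staining (PS2) follow, then a summary of resistant patients with 1-3 prior lines and PS2 of 50-100%. None of these is split or adjusted by eye-drop use.

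The same section defines the ocular events of special interest: "This subset includes TEAEs meeting criteria for the following terms: keratopathy and blurred vision".

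Protocol 5.8.2 is headed "Premedication with Corticosteroid Eye Drops (Dose Expansion Cohort#5 ONLY"), and protocol 2.3 gives the purpose as a secondary objective: "Evaluate the effectiveness of primary, prophylactic steroid eye drops in preventing or lessening keratopathy and/or blurred vision".

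Eligibility (protocol 3.1) differs across the three cohorts:
- Cohort 1: platinum resistant only, at most five prior regimens.
- Cohort 3: relapsed EOC, no upper limit on prior regimens.
- Cohort 5: "Patients must have received at least 3 but not more than 4 prior systemic treatment regimens".

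All three share the same FOLR1 threshold, at least 25% of tumor staining at 2+ or more.

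**The concern.** The pooled tables combine patients who differ by an intervention aimed at the very events being tabulated. A blended ocular rate describes neither group. The platinum-status table has a further problem, because the two columns cannot be expected to contain the same share of patients on drops. All 40 Cohort 1 patients go into the resistant column, and every sensitive patient must come from Cohort 3 or Cohort 5. If the drops work, a difference in ocular rate can appear between resistant and sensitive patients with no effect of platinum status behind it. A reader choosing a population or judging ocular risk could take a prophylaxis effect for a patient characteristic.

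**Working it through.** The plan gives no figure for this point, so there is nothing to reproduce. The possible bias can be sized with a mixing calculation.

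**Inputs**
- Planned sizes: Cohort 1 = 40, Cohort 3 = 20, Cohort 5 = 40 (SAP 2.3.3.2).
- Rates for illustration: 50% without and 30% with prophylaxis, from the blurred-vision planning statement for Cohort 5 (protocol synopsis, Sample Size).
- Assumed, because the documents do not give them: s3 and s5, the shares of Cohorts 3 and 5 that are platinum sensitive.
- No true effect of platinum status or prior lines.

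**Formula**
Expected rate in a column = 50 − 20 × (share of that column from Cohort 5).
- Resistant: 40 + 20(1 − s3) patients without drops, 40(1 − s5) with drops.
- Sensitive: 20·s3 without drops, 40·s5 with drops.

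All three cohorts together: (60 × 50 + 40 × 30)/100 = 42%, which is the rate of neither group.

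**Platinum status**

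| s3 | s5 | Resistant: drops/n | Rate | Sensitive: drops/n | Rate | Sensitive − resistant |
|---|---|---|---|---|---|---|
| 0.25 | 0.25 | 30/85 | 42.9% | 10/15 | 36.7% | −6.3 |
| 0.50 | 0.50 | 20/70 | 44.3% | 20/30 | 36.7% | −7.6 |
| 0.75 | 0.75 | 10/55 | 46.4% | 30/45 | 36.7% | −9.7 |
| 0.25 | 0 | 40/95 | 41.6% | 0/5 | 50.0% | +8.4 |
| 0.50 | 0 | 40/90 | 41.1% | 0/10 | 50.0% | +8.9 |
| 1.00 | 0 | 40/80 | 40.0% | 0/20 | 50.0% | +10.0 |

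The last three rows matter because Figure 3 and section 11.1 of the protocol describe Cohort 5 as platinum resistant. Its eligibility criteria, protocol 4.1.5 and SAP 2.3.2.2 describe relapsed EOC without that restriction.

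The difference vanishes only when both columns have the overall 40% share on drops. That requires 40·s5/(20·s3 + 40·s5) = 0.4, that is, s5 = s3/3.

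**Prior regimens**
Patients with 1-2 or with 5 or more regimens can come only from the cohorts without drops, but Cohort 5's 3 and 4 regimens fall on either side of the 1-3 versus >3 cut. Take all patients as platinum resistant for simplicity, and let f1, f3, f5 be the assumed shares with 1-3 regimens in Cohorts 1, 3 and 5.
- f = (0.5, 0.5, 0.5): 20/50 on drops in each column, 42% in both, difference 0.
- f = (0.5, 0.3, 0.7): 28/54 versus 12/46 on drops, 39.6% versus 44.8%, so 5.2 points lower with 1-3 regimens.
- f = (0.7, 0.5, 0.3): 12/50 versus 28/50 on drops, 45.2% versus 38.8%, so 6.4 points higher with 1-3 regimens.

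**PS2 bands**
The FOLR1 criterion is identical in the three cohorts, so eligibility creates no link between band and drop use. The ocular rate is blended, but no difference is forced.

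**After splitting by cohort group**
Under the same assumptions every cell without drops has 50% and every cell with drops has 30%, so the spurious difference is zero.

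**The case against.** The best defense is that the SAP already shows ocular events by cohort. Section 3.8 makes cohort or treatment group the default column, the dedicated ocular tables (incidence and grade, time to onset, action taken) sit outside the subgroup paragraph, and AE listings are sorted by cohort. The table shells are a separate document that cannot be seen here. This protects the reading of Cohort 5 itself, but it does not cure the subgroup tables. The default yields where a later section says otherwise, section 6.2 does so, and no planned table crosses cohort with these subgroups.

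It is also fair that the consequence is limited. The trial tests no formal hypothesis, and no objective compares ocular toxicity by platinum status or prior lines. In the 50% sensitive scenario, chance alone gives a standard error of √(0.367 × 0.633/30 + 0.443 × 0.557/70) ≈ 0.106, about 11 points, which is larger than the 7.6-point bias.

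The illustrative rates are soft too. The protocol synopsis attaches the same fall from 50% to 30% to Cohort 1, which had no prophylactic steroid drops and was enlarged to "better define the frequency and assess the impact of the proposed management guidelines for ocular adverse events". The documents therefore do not fix 50% as Cohort 1's rate. Therapeutic steroid drops are allowed in any cohort (protocol 5.8.8.2), so the contrast is prophylaxis versus none, not steroid exposure versus none.

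A reader might infer that Cohort 1 should also be split at Amendment 9, which made lubricating drops mandatory. The documents do not support that as a clean boundary. Amendment 7 had already added daily artificial tears for all patients and revised the eye-disorder guidelines. Patients already on treatment would be misclassified by first-dose date, and the dates on which sites implemented the amendment are not shown to be collected.

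**Conclusion.** The point holds for ocular TEAEs in the EOC subgroup tables. For platinum status the mixing is structural, because the all-resistant, unprophylaxed Cohort 1 can enter only one column. For prior regimens, confounding is possible, with either sign or none. For the PS2 bands and the summary of 1-3 prior lines with PS2 50-100%, the ocular rate is a blend and nothing more.

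The size rests on 50% versus 30%, on planned cohort sizes, and on a case mix that the documents do not give. Under those assumptions the rate in sensitive patients looks about 6 to 10 points lower if 25-75% of both Cohorts 3 and 5 are sensitive. It looks 8 to 10 points higher if Cohort 5 is all resistant and 25-100% of Cohort 3 is sensitive. A reader might settle on one number, such as 7.6 points, or conclude that all the subgroup comparisons are biased. Neither is supported: size and direction cannot be fixed from the documents, and staining bands are not tied to drop use.

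No primary endpoint is affected. This is an inexpensive improvement to descriptive tables.

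**What to change.** Add to SAP 6.2, under the EOC subgroup analyses: *In these tables the incidence and CTCAE grade of ocular TEAEs (keratopathy, blurred vision) will be shown separately for Cohort 5 and for Cohorts 1 and 3 combined. No comparison of ocular TEAEs by platinum status or number of prior regimens will be based on the pooled rate. Other TEAEs will be summarized with the three cohorts pooled.*

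Apply the same split to the PS2 tables and to the 1-3 prior lines/PS2 50-100% summary, so that the blended ocular rate is not read as that of either group. Time to onset and action taken need not be added by subgroup, since the SAP does not plan them there.

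The split uses cohort membership, which is already held, and works whichever description of Cohort 5 is correct. The cost is a sentence or two of SAP text, extra columns, and smaller denominators. In the 50% scenario the sensitive group of 30 becomes 10 without and 20 with drops.
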